*** Does this research study involve any of the following:**

Name

- Deception
- Interview/Focus Groups
- Use of Drug, biological, or nutritional (e.g., herbal or dietary) supplement (investigational or FDA approved)?
- Use of medical devices
- Prospective Analysis of Specimens
- Banking of Specimens-Data
- Retrospective use of specimens
- Audio/Video Recordings or Photographs
- Honest Broker or other similar service
- None of the Above**

ID: Pro00002952

View: 4 Research study methods

Research Study Methods

Describe all study related procedures following enrollment of a subject in this study.

Please see Section 6 for where the study team defines when a subject will be considered enrolled in the study.

1.0

*** Research Procedures/Interventions:**

Study Interventions:

Pulmonary Telerehabilitation Intervention Group: The intervention will consist of an eight-week, three sessions per week, home-based pulmonary telerehabilitation program that will incorporate both lower extremity endurance exercise and upper and lower extremity resistance training. **Subjects randomized to the study intervention will also participate in a optional once monthly support group via group phone call through a reserved VANTS line. This phone conferencing consisting of an educational topic (i.e. inhaler use, understanding COPD) and group discussion.** Participants randomized to the intervention arm will receive a tablet with VA Video Connect software installed for video conferencing, a portable cycle ergometer, and a set of exercise resistance bands of varying resistance (extra-light, light, medium, heavy, extra-heavy). **Patients will also be given an pedometer at hospital discharge to be worn everyday following discharge to track the patient's physical activity. Patients will receive a pedometer diary from study staff to record their daily steps from the pedometer.** We also contact participants by telephone weekly to document their pedometer count. They will be permitted to keep the pedometer, cycle ergometer and resistance bands, at the completion of the study.

For safety purposes, participants in both the intervention and usual care group will also be enrolled in the hospital's telehealth program, which consists of daily monitoring of pulse oximetry, heart rate, blood pressure, and weight and regular contact with a telehealth provider. They will receive a pulse oximeter, automated blood pressure cuff, and scale as part of this program. An exercise physiologist will meet with participants randomized to the intervention group prior to hospital discharge but after informed consent is obtained to conduct a minimum of one to two face-to-face inpatient bedside pulmonary rehabilitation sessions. These sessions will be used to guide development of an individualized exercise prescription, determine participant oxygen requirements with exercise, and to assess participant safety. **Within one to six weeks post-discharge, participants in the intervention arm will begin pulmonary tele rehabilitation** sessions via 1:1 video conferencing with the exercise physiologist/study coordinator. The exercise physiologist/study coordinator will be located at VAPHS during these video conferencing sessions. These sessions will consist of: (1) a brief pre-exercise interview to assess symptoms and vital signs (pulse oximetry, pulse, blood pressure); (2) a warm-up period consisting of upper and lower extremity stretching exercises; (3) cycle ergometry with resistance settings and goal duration determined by the individualized exercise program developed prior to hospital discharge; (4) upper and lower extremity strength training with resistance bands; (5) a post-exercise debriefing interview to assess symptoms and post-exercise vital signs. Subjects will be offered the opportunity to enroll in a traditional facility-based pulmonary rehabilitation program.

Usual Care Group: Participants randomized to the usual care arm will also be enrolled in our institution's telehealth program, will receive an automatic blood pressure monitor, portable pulse oximeter, and scale. **Patients randomized to Usual Care will also be given an pedometer at hospital discharge to be worn everyday following discharge to track the patient's physical activity. Patients will receive a pedometer diary from study staff to record their daily steps from the pedometer.** We

also contact participants by telephone weekly to document their pedometer count. They will be permitted to keep the pedometer at the completion of the study.

Participants will be in regular contact with a telehealth provider. A study team member will meet with participants randomized to the usual care arm prior to discharge but after informed consent is obtained to discuss the importance of exercise and will encourage exercise (strength training, light aerobic activity such as walking or cycling) a minimum of 20-40 minutes three times per week at discharge. **The usual care group will not receive a cycle ergometer or resistance bands and will not participate in the VANTS conference call support group. Patients randomized to the control group will be offered home telerehab enrollment following completion of the study.**

Subjects in both the intervention and usual care group will receive all of the necessary information needed to participate in regular pulmonary rehabilitation. If an enrolled subject arranges to begin participation in a facility-based pulmonary rehabilitation before the conclusion of the study period, the subject will need to contact the study team to discuss withdrawal from study participation.

Development of the Initial Exercise Prescription: The exercise prescription will be developed based on exercise performance and self-reported modified Borg dyspnea scores, a scale widely used in both the clinical and research setting to measure a patient's perceived shortness of breath and effort, during the six minute walk and bedside pulmonary rehabilitation sessions. During the bedside sessions, the exercise physiologist/study coordinator will select the resistance setting on the cycle ergometer that allows the participant to perform five minutes of lower extremity cycle ergometry while achieving Borg scale ratings between four and six in accordance with the American Thoracic Society (ATS)/European Respiratory Society (ERS) Guidelines. Alternatively, interval training, which has resulted in similar improvements in walk distance and quality of life scores, will be used for those participants unable to perform five minutes of cycle ergometry. During the resistance training exercises, the resistance band workload that causes fatigue after eight to twelve repetitions will be selected for each target muscle group. Exercise performance during these bedside sessions combined with heart rate and exercise performance during six minute walk will be used to develop an individualized exercise prescription for home pulmonary telerehabilitation. [name] will provide guidance as needed on developing the initial exercise prescription for each participant.

Modification of the Exercise Prescription: The exercise prescription will be adjusted during the eight-week intervention to achieve modified Borg dyspnea scores of four to six during cycle ergometry and to target one to three sets of eight to twelve repetitions of each resistance training exercise per established guidelines. The resistance band level will be increased when a participant is able to complete three sets of twelve repetitions using correct technique through the full range of motion. [name] will provide guidance as needed on modification of the individualized exercise prescriptions throughout the eight-week intervention for each participant based on their performance. Other factors, including heart rate and blood pressure during exercise, will be considered when modifying the exercise prescriptions.

Measurement of physical activity: Participant activity will be measured with an pedometer provided at hospital discharge. The pedometer will be worn every day to track the participant's physical activity.

Safety and Oxygen Monitoring: Oxygen saturations will be continuously monitored during the six minute walk testing and inpatient bedside pulmonary rehabilitation sessions. Any participant demonstrating oxygen desaturations during these activities will undergo a formal exercise desaturation study to determine oxygen requirements prior to hospital discharge. In addition, vital signs will be monitored before, during, and after each bedside pulmonary rehabilitation session. These sessions will allow investigators to assess participant safety with exercise and to disqualify any participants that are unable to participate safely in endurance and/or resistance training. Finally, participants will be provided an automated blood pressure cuff and pulse oximeter to allow for intermittent monitoring of blood pressure and continuous monitoring of oxygen saturation and heart rate during the home pulmonary telerehabilitation sessions. Prior studies have shown home-based pulmonary telerehabilitation programs to be safe, even in severe COPD. However, if the exercise physiologist has any concern with participant safety during the home-based telerehabilitation sessions, emergency services will be immediately contacted.

Handgrip and quadriceps muscle strength testing: Handgrip strength of the dominant hand will be measured with a hand dynamometer. Three measurements will be taken with a 60 second recovery period between trials. The average maximal force across trials will be calculated as the final handgrip strength. Quadriceps muscle maximal force (kilogram-force, kgf) will be measured with a Keiser leg press, equipment available in [name] research center, in those participants willing to return within approximately one week post-discharge for muscle strength measurements. This test will be optional. One repetition maximum (1RM) measures will be obtained by progressively increasing resistance until the participant is unable to successfully complete one repetition. Peak muscle power will be measured at 40, 50, 60, 70, 80, and 90 percent of the 1RM 30 minutes after the 1RM measurement was obtained.

Six Minute Walk testing:

A six minute walk test will be performed by a study member. Data from the six minute walk test (distance walked, blood pressure and heart rate pre/post-procedure, symptoms pre, post-procedure) will be recorded on a de-identified study form, kept in the participant's de-identified study chart, and entered into the study data base. The six minute walk test is a validated, simple test that is responsive to changes in exercise endurance following pulmonary rehabilitation in COPD patients both during stable disease and following acute exacerbations. Exercise capacity will be defined by the six minute walk test. The six minute walk will be repeated following eight weeks of either the pulmonary telerehabilitation intervention or usual care. Participants' perception of dyspnea and exertion will be assessed at the end of the six minute walk testing with the ten point Borg dyspnea and leg fatigue scale, which ask about the degree of shortness of breath and leg fatigue. The six-minute walk test is an easy to perform and practical test that measures the distance that a patient can walk on a flat, hard surface in a period of six minutes.

Sit-to-stand testing: The one-minute sit-to-stand test has been shown to be reliable, valid, and responsive to change in exercise capacity following pulmonary rehabilitation in individuals with COPD. The test consists of the participant standing at full leg extension from a sitting position at their own pace as

often as possible during a one minute testing interval. The participant is permitted to stop at any time during the one minute interval if necessary. An armless chair is used for testing and the participant is asked to fold their arms across their chest during testing. **One test will be performed prior to discharge and another sit to stand will be performed following eight weeks of either the pulmonary telerehabilitation intervention or usual care.** The participants' perception of dyspnea and exertion will be assessed following each test with the ten point Borg dyspnea and leg fatigue scale.

Health-related quality of life assessments: Health-related quality of life will be assessed with the St. George's Respiratory Questionnaire (SGRQ) and the Short-Form 36-Item Questionnaire (SF-36) prior to hospital discharge and following eight weeks of either the pulmonary telerehabilitation intervention or usual care. The SGRQ is a disease-specific questionnaire validated to measure health status in patients with COPD. Total SGRQ scores range from 0-100 with higher scores indicating greater symptoms burden. The minimal clinically important difference is a difference of four points in the total SGRQ score. The SF-36 consists of 36 questions spanning nine health domains and is a valid measure of health-related quality of life in COPD that is responsive to change following a pulmonary rehabilitation intervention.

Participant satisfaction survey: Participants will be administered a survey by the study coordinator after completion of the eight-week pulmonary telerehabilitation intervention that will require them to respond to statements related to their satisfaction with the home-based program using a five point Likert scale (strongly agree, agree, neutral, disagree, strongly disagree). Statements will address ease of use of the video conferencing modality, acceptability of exercise components, perceptions of impact on muscle strength and exercise endurance, and willingness to participate in additional pulmonary telerehabilitation. Questions regarding social support, psychiatric attributes, and other factors potentially associated with program adherence will also be asked in order to gain preliminary insights to optimize recruitment for a larger, randomized controlled trial of pulmonary telerehabilitation.

Please upload a table of procedures if applicable.

The study procedures table must be completed for:

- All Greater than Minimal Risk (GTM) studies; and
- All Minimal Risk studies that use Standard of Care or Usual Care/Interventions.

Name	Modified Date
Table of procedures	3/2/2021 12:56 PM

2.0

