The distributional characteristics of the outcome measures and change in outcome measures between study groups will be determined using appropriate descriptive statistics (e.g. mean, median, standard deviation, range) and graphical summarizations (e.g. histograms, boxplots, line plots). The purpose of this pilot study is to generate preliminary data on the expected effect size and variance of the outcome measures to facilitate planning (i.e. sample size calculations and power analyses) of a larger, randomized controlled trial. As such, we acknowledge that, given our small sample size (n=30, 15 participants per group), we likely will not have the power to detect a significant statistical or clinical difference in outcome measures between the intervention and usual care groups. However, we will perform exploratory analyses to compare changes in outcome measures between groups using a Student's t-test or nonparametric tests when appropriate.

ID: Pro00002952

View: 5 Sub-Studies

1.0 * Is there a sub-study or are there sub-studies associated with this study?

There is no sub-study associated with this study.

ID: Pro00002952

View: 6 Study Population Summary

Study Population Summary

1.0 * What is the maximum number of subjects you plan to enroll at VAPHS?

We plan to enroll 38 participants, accounting for 25% attrition, to result in 30 participants (15 intervention, 15 control) completing baseline and eight-week follow up testing.

2.0

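### Pedometer baseline: steps are first counted after randomisation and after pre-discharge contact that differs by arm, so change from baseline is the wrong summary for steps

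*Combined protocol and SAP*

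**What the plan says.** **Outcome.** Study Objectives, SA 2 (View 2) lists pedometer activity among the measures compared as change from baseline. It says that their effect size and variance will be used to plan a larger trial. The Analysis Plan (View 4.1) says "we will perform exploratory analyses to compare changes in outcome measures between groups". Neither place defines the step baseline or the weeks to be analysed.

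**Order of events.** Study Population Summary, item 2.0 (View 6) places randomisation before discharge. The arm-specific contact described in Research Procedures/Interventions (View 4, item 1.0) then follows, also before discharge:

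- *Usual care:* a study team member talks about why being active matters. The same person "will encourage exercise (strength training, light aerobic activity such as walking or cycling) a minimum of 20-40 minutes three times per week at discharge".
- *Telerehabilitation:* "An exercise physiologist will meet with participants randomized to the intervention group prior to hospital discharge" for at least one to two bedside sessions. Performance there and in the six-minute walk is "used to develop an individualized exercise prescription for home pulmonary telerehabilitation". This arm also receives a cycle ergometer and resistance bands, with no delivery date given.

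**Step counting.** "Participant activity will be measured with an pedometer provided at hospital discharge". In both arms it is "to be worn everyday following discharge to track the patient's physical activity", and staff collect the counts weekly by telephone.

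**Start of the programme.** "Within one to six weeks post-discharge, participants in the intervention arm will begin pulmonary tele rehabilitation" sessions by video.

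**The concern.** A baseline is useful because the treatment cannot yet have affected it. Here every step count in either arm comes after allocation and after contact that could change how much people walk. Usual-care participants have been encouraged to exercise, with walking named as an example. Telerehabilitation participants have exercised at the bedside and have a prescription, but on the wording of the intervention section their programme is still at least a week away.

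The most natural choice of baseline, first-week steps, therefore compares one arm already encouraged to be active with another that is waiting. Subtracting it removes part of the effect of assignment, in a direction nobody can state. What is at stake is one of the pilot's deliverables: the step effect size and variance passed to the larger trial. The optional leg press, about one week after discharge, also follows the unequal contact. The sit-to-stand test and the questionnaires are first done before discharge, so the point mainly concerns steps.

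**Working it through.** The plan has no figure of its own to reproduce: Study Population Summary, item 4.0 says no sample size calculation was made. The documents give no step mean, step SD or effect of advice.

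**Inputs.** Wait *t* = 1 to 6 weeks and an eight-week programme (Research Procedures/Interventions); 15 per arm (Analysis Plan). Assumptions: the talk raises usual-care steps by *a* = 0.1 to 0.3 SD, and the SD is the same in all weeks.

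**1. What change from the first week estimates.** Let T1 and U1 be mean first-week steps in the telerehabilitation and usual-care arms, and TP and UP the programme-week means. Then

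(TP − T1) − (UP − U1) = (TP − UP) − (T1 − U1).

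Apart from chance, randomisation makes T1 − U1 zero unless arm-specific contact has moved it. So the change contrast equals the level contrast minus the early difference that contact produced. If the talk raises U1 by *a*, and the bedside sessions, prescription and equipment raise T1 by *b*, the amount added is *a* − *b*. Its sign is unknown.

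**2. The talk alone (*b* = 0), under three possible step summaries.**

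| Summary | Effect confined to the wait | Effect lasts in full |
|---|---|---|
| Average over the whole record, *t* + 8 weeks | −*a* × *t*/(*t* + 8) | −*a* |
| Change from first week to programme weeks | +*a* | 0 |
| Programme-week levels | 0 | −*a* |

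The waiting share *t*/(*t* + 8) is 1/9 = 0.11, 3.5/11.5 = 0.30 and 6/14 = 0.43 at waits of 1, 3.5 and 6 weeks.

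- *Confined to the wait:* the whole-record average shifts by −0.111 × 0.1 = −0.01 SD to −0.429 × 0.3 = −0.13 SD, and the change from week one by +0.10 to +0.30 SD.
- *Lasting in full:* the whole-record average and the programme-week levels shift by −0.10 to −0.30 SD, and the change from week one by 0.

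None of these ranges is a bound, because *a* is assumed and *b* is unknown. The sign depends on analysis choices the plan leaves open.

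**3. Scale.** The standard error of a difference in levels is √(2/15) = 0.365 SD. For change scores with within-person correlation ρ it is 0.365 × √(2(1 − ρ)). This is 0.365 at ρ = 0.5 and 0.365 × √0.68 = 0.30 at ρ = 0.66. A shift of 0.30 SD in the change contrast is therefore below one standard error unless ρ exceeds about 0.66.

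**4. Weeks available for a matched comparison.** Participant Payments, item 1.0 (View 12.2) can be read as ending pedometer wear eight weeks after discharge. Usual-care counts would then overlap 8 − *t* of the eight programme weeks: 7, 4.5 and 2 at waits of 1, 3.5 and 6 weeks.

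**The case against.** The strongest reply is that the talk is part of the comparator. Supervised rehabilitation against exercise advice is a legitimate comparison, and the telerehabilitation arm gets more before discharge. The reply adds:

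- The table of procedures, the visit checklists and the home-based rehabilitation form are uploads not reproduced in the text. Any of them may tell participants what to do while waiting.
- The Abstract speaks of starting at discharge, so a wait of a week or more rests on the intervention section's wording.
- The undefined baseline and variable start would be gaps without any talk.
- With 15 per arm, change from baseline guards against chance imbalance.
- The plan already concedes low power and calls its tests exploratory.

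Most of this stands. It rules out two stronger readings that a reader might infer. One is that the talk biases the trial against telerehabilitation: the net effect *a* − *b* has no known sign. The other is that the telerehabilitation arm leaves hospital without exercise guidance: it has bedside sessions and a prescription, and the text is merely silent about the wait.

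The reply does not answer the narrower point. A comparator may include advice, but a measurement taken after that advice is not a baseline. Subtracting it removes real early differences along with chance ones.

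**Conclusion.** The point holds as a minor one, mainly for steps. On the text provided, no step baseline precedes randomisation or arm-specific contact, so the planned change contrast would subtract any early difference between arms. Neither the direction nor the size of the distortion can be determined. The illustrative +0.10 to +0.30 SD requires the assumed *a*, an effect confined to the wait, and no offset from the bedside sessions, prescription and equipment. The documents do not support calling the talk an error or predicting whom it favours. The point is still worth acting on because the step estimate and its variance are meant for planning a larger trial.

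**What to change.** For steps, replace change from baseline with a comparison of step levels between the randomised arms by week since discharge, over the weeks recorded in both arms. Report weeks from discharge to first session separately from programme weeks. Treat that split as descriptive, since usual care has no first-session date and start dates vary.

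This uses weekly counts already collected, plus each participant's first-session date. The cost is a little more analysis. Late starters contribute few overlapping programme weeks if usual-care wear stops at eight weeks. Some precision is also lost relative to change scores if ρ is above 0.5.

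Giving both arms the same brief encouragement before discharge is optional. In the telerehabilitation arm it should follow the bedside safety assessment, which lets investigators "disqualify any participants that are unable to participate safely in endurance and/or resistance training". Extending usual-care step recording to week 14 (six-week wait plus eight programme weeks) is not required. It would add wear burden and calls, and could delay the telerehabilitation offered to controls afterwards.

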(1) Acute hypercapneic respiratory failure with a requirement for invasive mechanical ventilation during hospitalization; (2) A diagnosis of myocardial infarction during hospitalization or unstable cardiac or neurologic disease at discharge; (3) Currently enrolled in a pulmonary rehabilitation program or completion of a pulmonary rehabilitation program within the past 6 months; (4) A medical condition that makes exercise unsafe (includes upper and lower limb strength training and lower limb cycle ergometry). This will be determined by the following- screen for these through chart review, discussion with the patient (do they have any known cardiac issues, do they have chest pain with exertion, are they lightheaded with exertion), discussion with the physicians caring for the patient in the hospital, and direct observation and assessment during the bedside pulmonary rehab sessions (that were built into this study for safety purposes). (5) Inclusion in another greater than minimal risk study. Exclusion criteria were selected to minimize bias and to maximize patient safety when participating in a home-based exercise program.

4.0 If there are any age, ethnic, language, or gender-based exclusion criteria, including the exclusion of any pregnant or lactating women, or those of child-bearing potential, please provide justification:

The age range of 40-80 was selected in order to select for COPD patients with significant pulmonary disease that fall within an age range where age-related changes in muscle function are not the dominating factor.

5.0 Please specify why vulnerable subjects and/or special populations will not be enrolled:

6.0 With some exceptions as listed in VHA Handbook 1200.05, incompetent subjects cannot be enrolled in VAPHS approved research. Specify that you will not enroll incompetent subjects and the general rules to be used in making that determination:
We will not enroll incompetent subjects.

ID: Pro00002952

View: 7 Risk/Benefit Assessment-Risks

Risk/Benefit Assessment-Risks

1.0 * Risk classification for this study (select one).

Name
 Minimal Risk
 Greater than Minimal Risk

2.0 * Basis for making the above recommendation:

The participants will be undergoing an exercise intervention as well as muscle strength testing and six minute walk testing, all of which are greater than minimal risk procedures.

3.0 * Describe the safety precautions that will be taken to minimize risks/harms:

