Oxygen saturations will be continuously monitored during the six minute walk testing and inpatient bedside pulmonary rehabilitation sessions. Any participant demonstrating oxygen desaturations during these activities will undergo a formal exercise desaturation study to determine oxygen requirements prior to hospital discharge. In addition, vital signs will be monitored before, during, and after each bedside pulmonary rehabilitation session. These sessions will allow investigators to assess participant safety with exercise and to disqualify any participants that are unable to participate safely in endurance and/or resistance training. Finally, participants will be provided an automated blood pressure cuff and pulse oximeter to allow for intermittent monitoring of blood pressure and continuous monitoring of oxygen saturation and heart rate during the home pulmonary telerehabilitation sessions. Prior studies have shown home-based pulmonary telerehabilitation programs to be safe, even in severe COPD. However, if the exercise physiologist has any concern with participant safety during the home-based telerehabilitation sessions, emergency services will be immediately contacted.

4.0 * Provide details regarding the nature of each risk using the area provided below:

Risk Name
View Questionnaires
View Pedometer
View Measurement of handgrip and quadriceps strength
View Sit-to-stand testing
View Participating in the pulmonary telerehabilitation program
View Six Minute walk

5.0

*** Do you plan on using the research answering service:** Yes No

If yes, please Upload the research answering service form:

[Research Answering Service - SPiRE.doc\(0.01\)](#)

6.0 If your study involves a treatment or intervention, please upload the Patient ID Card:

ID: Pro00002952

View: 7.1 Risk/Benefit Analysis-Potential Benefits and Alternatives

Risk/Benefit Analysis-Potential Benefits and Alternatives

Describe any potential for benefits to participants in this study:

1.0 * Direct and Indirect Benefits to Subjects:

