We will follow the following procedures to identify subjects and determine eligibility: (1) We will review the inpatient admission and census lists each day for all patients admitted to the inpatient wards (non-critical care units) with a primary diagnosis of COPD. The medicine teams will also be asked to contact the study team if they have a patient that meets eligibility criteria and is interested in the study. We will also review inpatient censuses with the charge nurses to identify potential subjects. We will also be alerted by the pulmonary fellow or pulmonary attending if a patient with an acute exacerbation of COPD is referred to the pulmonary inpatient consult service (2) We will review the charts for inclusion and exclusion criteria (HIPAA authorization waiver requested) (3) When subject eligibility is determined, the health care team caring for the patient will be notified and asked to approach the patient, introduce the study, and ask if someone from the study team can come and discuss the study with them (4) For interested patients, we will meet with them at bedside in the hospital and review inclusion/exclusion criteria to confirm eligibility. Once eligibility and willingness to participate is confirmed, the subjects will undergo the written informed consent process.

3.0

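### An exercise-safety exclusion can be applied after randomisation in the telerehabilitation arm only, and the supplied text does not say what then happens to the participant's follow-up, analysis or place in the adherence count

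*Combined protocol and SAP*

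**What the plan says.** Exclusion criterion 4 (Study Population, View 6.1, item 3.0) covers conditions that make exercise unsafe. It is determined in several ways. Investigators "screen for these through chart review, discussion with the patient" and with the treating physicians, and they also use "direct observation and assessment during the bedside pulmonary rehab sessions".

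The safety paragraph under Research Procedures/Interventions (View 4, item 1.0) says the bedside sessions let investigators "disqualify any participants that are unable to participate safely in endurance and/or resistance training". The Risk/Benefit section (View 7, item 3.0) repeats it: "These sessions will allow investigators to assess participant safety with exercise and to disqualify any participants".

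View 4 also says who has these sessions: "An exercise physiologist will meet with participants randomized to the intervention group prior to hospital discharge but after informed consent is obtained". The usual care arm has a pre-discharge meeting, whose stated purpose is "to discuss the importance of exercise and will encourage exercise". No bedside exercise session is described for that arm.

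The recruitment section (View 8, item 2.0) puts eligibility earlier: "Once eligibility and willingness to participate is confirmed, the subjects will undergo the written informed consent process". The consent section (View 9.4, item 3.0) adds that no procedure takes place before written consent. The Study Population Summary (View 6, item 2.0) speaks of randomising eligible participants before discharge.

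The analysis plan (View 4.1) compares changes between groups by t-test or nonparametric test and names no analysis set. The phrase 'intention to treat' occurs once, in the Brief Description, attached to the programme. Specific Aim 1 tracks adherence without saying who is counted. Participant Payments (View 12.2) gives 24 sessions per intervention participant.

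**The concern.** Eligibility should be settled before allocation, or by a check that is the same in both arms. Here one component of an exclusion criterion can be observed only at a procedure that follows consent and, as described, follows randomisation to one arm. The text does not say whether 'disqualify' means stopping exercise or leaving the study.

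Two of the pilot's outputs depend on the answer. Specific Aim 2 supplies an effect size and variance for planning a larger trial. If those found unable to exercise safely leave follow-up or analysis in one arm while their counterparts stay in the other, that comparison is no longer between the groups as randomised. Specific Aim 1 supplies adherence. If those participants drop out of the count, the figure describes people cleared to exercise, not everyone to whom the programme was allocated. A larger trial would need the second figure to plan recruitment and delivery.

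**Working it through.** **Sequence, from the sections side by side**

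1. View 8: eligibility is confirmed, then consent is taken.
2. View 9.4: no procedure precedes consent, so a bedside session cannot contribute to step 1.
3. View 4: the sessions are given to participants randomised to the intervention, so they also follow allocation.
4. View 6.1: observation in those sessions helps determine exclusion criterion 4.
5. Views 4 and 7: the sessions can lead to disqualification.
6. View 4: usual care has a discussion instead.

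Steps 1 and 4 cannot both hold as written. Steps 3 to 6 together give an exclusion that operates after randomisation in one arm.

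**Adherence illustration**

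The documents give no disqualification rate and no expected attendance, so there is no plan figure to reproduce. From the documents: 24 sessions, and an arm of 19 (half of the 38 to be enrolled) or 15 (half of 30). Assumed: 1 or 2 disqualified, and attendance *a* = 0.80 among those cleared.

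Adherence over all allocated = *a* × (n − k)/n.

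| n | k | (n − k)/n | Among those cleared | Over all allocated |
|---|---|---|---|---|
| 19 | 1 | 0.947 | 80% | 0.80 × 18/19 = 75.8% |
| 19 | 2 | 0.895 | 80% | 0.80 × 17/19 = 71.6% |
| 15 | 1 | 0.933 | 80% | 0.80 × 14/15 = 74.7% |
| 15 | 2 | 0.867 | 80% | 0.80 × 13/15 = 69.3% |

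In sessions, for 2 of 19: 17 × 24 = 408 scheduled for those cleared, and 0.80 × 408 = 326.4 attended. Over all allocated, 19 × 24 = 456, and 326.4/456 = 71.6%. The ratio (n − k)/n does not depend on the 80%.

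**Between-arm change, illustration only**

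This applies only if disqualified participants leave the analysis. Assume an absolute correlation ρ of 0.3 to 0.7 between the trait that leads to removal and the eight-week change. The arm mean then shifts by about ρ × φ(z_f)/(1 − f) standard deviations, where f = k/n, φ is the normal density and z_f the normal quantile at f.

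- n = 19: factors 0.113 (k = 1) and 0.204 (k = 2). The range is 0.3 × 0.113 = 0.03 to 0.7 × 0.204 = 0.14 SD.
- n = 15: factors 0.139 and 0.248. The range is 0.3 × 0.139 = 0.04 to 0.7 × 0.248 = 0.17 SD.
- Simulation of dropping the k lowest of n gives factors of 0.103 and 0.190 (n = 19), and 0.124 and 0.230 (n = 15), so these shifts are slightly high.
- The standard error of the difference is √(2/19) = 0.32 SD or √(2/15) = 0.37 SD.

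The largest assumed case is 0.174/0.365 = 0.48 of a standard error. With zero correlation the shift is nil. The sign is not determined by the documents.

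**The case against.** The strongest reply is that no section says data are lost. View 4 sets the six-minute walk, sit-to-stand test and questionnaires after eight weeks of either arm, with no exception for someone who stops exercising, and the Brief Description uses the phrase intention to treat. If 'disqualify' means only stopping exercise, the comparison stays intact. This stands, and the bias is therefore conditional. It does not remove the one-arm check, and placing the observation among the exclusion criteria points the other way.

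Second, the check is residual. Chart review, patient interview and physician discussion can screen both arms, and both arms do a six-minute walk and a sit-to-stand test at baseline. Interval training "will be used for those participants unable to perform five minutes of cycle ergometry", so limited endurance alone need not lead to disqualification. This stands too, and the number affected may well be small. The documents do not say that the baseline tests disqualify anyone; desaturation leads to an oxygen evaluation.

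Third, adherence among starters is a legitimate measure of a home-based programme. Agreed, if it is labelled as such, but it answers a narrower question than feasibility among all allocated.

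Fourth, the uploaded table of procedures, screening sheet, visit checklists, consent form and monitoring charter are not reproduced and may define what follows. That limits any claim about what is undefined. It does not resolve the conflict between the sections that are supplied.

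**Conclusion.** The point holds as a contradiction in the order of eligibility assessment and randomisation, together with an undefined consequence. It merits a cheap improvement.

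A reader might infer that the plan drops disqualified participants, and so biases the comparison in favour of telerehabilitation. The documents support neither step: they do not say that such participants leave, and they give no link between inability to exercise safely and change over eight weeks. A reader might also infer that usual care is not screened for exercise safety at all, which is wrong for the reasons given under the objection.

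On size, the adherence figure is the more tangible consequence. Under the assumed inputs it falls by about 4 to 11 percentage points when all allocated participants are counted. The shift in the between-arm change cannot be sized from the documents. Under the assumptions shown it stays below half a standard error, in comparisons that the plan itself calls exploratory and expects to lack power.

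**What to change.** Leave the clinical safety judgement, and the choice of assessments that inform it, to the investigators.

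1. Reconcile View 4 (intervention arm and safety paragraphs), View 6.1 (criterion 4), View 7 and View 8 on whether eligibility is complete before randomisation, and state what 'disqualify' means.
2. For anyone disqualified after randomisation, continue the already planned eight-week follow-up (questionnaires, pedometer and any test judged safe) unless consent is withdrawn.
3. State in the analysis plan (View 4.1) that arms are compared as randomised, using all available data.
4. Report the number disqualified, with reasons.
5. Report adherence out of 24 sessions over all randomised to telerehabilitation, alongside adherence among those who started, each labelled.

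The cost is a few sentences and the follow-up of a few participants who have stopped exercising. The price in results is a less favourable adherence figure and some dilution of the estimated effect.
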